8 ASSESSMENT OF SAFETY

PregSense™ is a passive “listening” tool - there is no energy transmitted into the body (unlike ultrasound and Doppler). The sensor communicates with the smartphone/tablet via Bluetooth. Bluetooth is a standard very common, low-energy communication technology.

8.1 Safety parameters

Subjects must be carefully monitored for adverse events. Adverse events should be assessed in terms of their seriousness, intensity, duration, resolution status and relatedness to PregSense™ usage. The outcome of each adverse event must be observed and documented.

8.2 Adverse events

There are no known adverse events related to the use of PregSense™, however, there are possible adverse events related to monitoring systems which involve sensor application on the skin. These include the following:

- Edema
- Erythema
- Irritation
- Sensitization

An adverse event is any undesirable experience (sign, symptom, illness, abnormal laboratory value, or other medical event) occurring to a subject, user or a third person, that appears or worsens during a clinical trial. An adverse event may or may not be related to the investigational device prescribed as part of the trial protocol.

8.2.1 Severity definition:

- Mild: AE which is easily tolerated
- Moderate: AE sufficiently discomforting to interfere with daily activity
- Severe: AE which prevents normal daily activities

The Primary Investigator (PI) will document in his opinion the relationship of the AE to the investigational product (medical device) using the criteria outlined below:

8.2.2 Relationship of an adverse event to the Treatment/ Device

- Unrelated: The AE has no temporal relationship to study device, and/or there is evidence of alternative cause such as concurrent medication or illness.
- Possibly related: A temporal relationship with study device is not clear, alternative causes are also possible.
- Probably related: A clear cut temporal relationship to the use of study device and potential alternative etiology is not apparent.
- Definitely related: A clear cut temporal relationship to the use of study device and no other possible cause.

8.3 Adverse Events (AE) and Severe Adverse Events (SAE) Reporting

The following shall apply to events occurring throughout the trial:

All severe adverse events (SAE) must be reported to the Sponsor within 24 hours after the investigator learns of the event, by faxing/e-mailing the completed Adverse Event Form.

The contact information for reporting to the Sponsor is as follows:

Nuvo Group Ltd.
[name]
[name]
[contact]
Email: [contact]

The sponsor is required to submit a full SAE report as applicable per regulations in each country. A full investigation and report must be submitted by the sponsor to the FDA and to local MOH as applicable, and/or to all reviewing IRBs/EC as soon as possible, but no later than 5 calendar days after the investigator first learns of the unanticipated severe adverse event. Thereafter, the Sponsor must submit any additional reports concerning the event, as FDA/MOH requests.

All other events, including technical failures, will be reported to the Sponsor every monitoring visit, confirmed in writing by the PI and recorded in the Case Report Form

Adverse events occurring in subjects enrolled, user or a third person in the trial must be evaluated and documented in the CRF and will be reviewed by the Sponsor upon every monitoring visit and, as applicable, reported to the Institutional Review Board (IRB) and other appropriate parties per country regulations.

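### Section 8.3 ties both expedited safety reports to the intensity grade *severe*; *serious* is not defined, so on a literal reading a serious event graded mild or moderate meets neither trigger

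*Combined protocol and SAP*

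**What the plan says.** Section 8.3, whose heading also expands SAE as severe, sets three reporting routes.

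- Site to sponsor, expedited: "All severe adverse events (SAE) must be reported to the Sponsor within 24 hours after the investigator learns of the event".
- Sponsor to authorities and IRBs/ECs, expedited: as soon as possible, and "no later than 5 calendar days after the investigator first learns of the unanticipated severe adverse event".
- Everything else: "All other events, including technical failures, will be reported to the Sponsor every monitoring visit".

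It also says: "The sponsor is required to submit a full SAE report as applicable per regulations in each country".

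Section 8.2.1 defines the grades by tolerance and daily activity. The top grade is "Severe: AE which prevents normal daily activities" and the one below it is "Moderate: AE sufficiently discomforting to interfere with daily activity". Section 8.1 lists seriousness and intensity as two attributes: "Adverse events should be assessed in terms of their seriousness, intensity, duration, resolution status and relatedness". Section 9.6.4.3 tabulates events by seriousness and by severity. The safety endpoints in the Synopsis, 4.2 and 9.2.2 refer to serious events. Section 12.3 expands SAEs as serious or unanticipated. SAE is missing from the List of Abbreviations.

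**The concern.** Seriousness and severity are different properties of an event, and sections 8.1 and 9.6.4.3 treat them so. Section 8.3 then attaches both clocks to severity. A site that reads section 8 in order meets the intensity definition of severe just before the reporting rule and has no criteria for serious to set beside it. The event at risk is one that is serious but graded mild or moderate: the rule as written does not require the site to tell the sponsor within 24 hours. A severe event that is not serious is expedited. What is at stake is timely notice to the sponsor in a study of pregnant women run at up to five centers in three countries.

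**Working it through.** No arithmetic applies. The plan gives no figure here to reproduce, so the check is to apply the wording of 8.2.1 and 8.3 to each kind of event.

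| Event | 24-hour report | 5-day report, if unanticipated | Route under 8.3 |
|---|---|---|---|
| Serious, graded severe | yes | yes | expedited |
| Serious, graded mild or moderate | no | no | next monitoring visit |
| Not serious, graded severe | yes | yes | expedited |
| Not serious, graded mild or moderate | no | no | next monitoring visit |

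The gap is the second row only. A serious event that also prevents normal activities is graded severe and is caught.

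Fetal events show how the second row could be filled. The adverse event definition covers events "occurring to a subject, user or a third person" and does not say how a fetal event is classified. The grades describe tolerance and daily activity, which do not apply to a fetus. Nothing in them requires a fetal event without maternal symptoms to be called severe.

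The monitoring-visit route has no fixed interval. Section 10.2 lets visit frequency vary by site and leaves it to the monitoring plan.

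The other routes are these:

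- Section 5.1: the sponsor reviews adverse events continuously. No time limit is given for an event to reach the sponsor.
- Section 3.5.2: the study App accepts event entries in real time. The text does not link these entries to the sponsor's review or to a deadline.
- Section 8.3: the country-regulation wording governs the sponsor's report and, in the last paragraph, onward reporting to IRBs and other parties. It sets no site-to-sponsor deadline.
- Section 12.3: serious or unanticipated events go to the EC/IRB, and the sponsor receives a copy of EC/IRB reports. No deadline is given, and the duty rests on the undefined word.
- Section 14: device failures and malfunctions are reported to the sponsor within 24 hours. This is a real deadline, but only for failures. Section 8.3 itself places technical failures in the monitoring-visit group, so those two statements also need reconciling.
- Sections 9.6.1 and 12.1: ISO 14155 is cited in both, and 21 CFR Part 812 in 12.1. Neither section brings a definition of serious into the text.

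**The case against.** The strongest reply is that severe in 8.3 is a slip for serious. The abbreviation is SAE, 12.3 expands it with serious, and 8.1 and 9.6.4.3 separate the two ideas. Experienced sites would probably apply the usual regulatory meaning. This is likely right about intent, and it limits the finding to a literal reading. It does not remove the need for correction, because severe appears in the heading and in both triggers and is the only one of the two words with a definition.

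The second reply is that the other routes, above all the sponsor's continuous review and the 24-hour failure report, make the gap narrower than 8.3 alone suggests. That stands. A reader might infer that serious events could go unreported altogether; given these routes, the documents do not support that.

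The third reply is that exposure is small. The device is passive, participation is up to 2 hours per subject, the listed possible reactions are skin reactions, and the feasibility study reported no adverse events in 76 subjects and 510 sessions. That also stands, and it is a reason to claim no event count.

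A reader might further infer a delay of weeks. The documents do not support a figure. They give no visit interval, and the 24-hour clock starts when the investigator learns of the event, so time from event to visit is not a like-for-like comparison. Nor do they show that the safety tables would change: all events enter the CRF, with seriousness and intensity assessed separately. What is missing there is a stated rule for classifying seriousness.

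**Conclusion.** The reporting rule is wrong as written and should be corrected. Confidence is high on the wording: both triggers name an intensity grade, the protocol elsewhere separates that grade from seriousness, and serious is not defined in the supplied text. The consequence rests on a literal reading and is confined to serious events graded mild or moderate. For those, no provision sets a deadline for the site to notify the sponsor, except where the event arises from a device failure. Size cannot be given, because the documents support neither a delay nor an expected number of events.

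Two limits apply. Some front pages were removed, and the Adverse Event Form, CRF, Operations Manual and Investigator Brochure are not among the documents, so a definition may exist there. If it does, the protocol should still carry it or point to it.

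**What to change.** Reconcile 8.2.1, 8.3, 9.2.2, 9.6.4.3 and 12.3 by amendment:

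1. In 8.3 and its heading, make both expedited triggers cover serious events, keeping the unanticipated condition for the 5-day report.
2. Define serious consistently with ISO 14155, which the protocol already cites. Keep it separate from the severity grade and say how it applies to fetal events.
3. State explicitly whether severe events that are not serious keep the 24-hour report they now have. Simply swapping the word would end that report without saying so.
4. Add SAE to the List of Abbreviations with a single expansion, and reconcile 8.3 with section 14 on the timing of technical failure reports.

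The cost is a wording amendment with EC/IRB approval and a check that the Adverse Event Form and CRF record seriousness and severity in separate fields. Enrolment, analysis sets and statistical methods are unaffected.

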9 STATISTICAL CONSIDERATIONS

9.1 Study Design and objectives

This will be a prospective, comparative, open label, multicenter study with test and reference devices used in each subject. The purpose of this study is to demonstrate safety and performance of PregSense.

9.2 Study Endpoint Measures

9.2.1 Primary Performance Measures

Fetal heart rate (FHR) as measured by PregSense™ versus the standard of care (i.e. CTG).

Maternal heart rate (MHR) as measured by PregSense™ versus the standard of care (i.e. CTG).

Both parameters are measured continuously for a duration of 30 minutes with data sampling taken at 1-minute intervals in parallel with both study devices.

9.2.2 Safety Endpoint Measures

Incidence of device related and/or protocol procedure related adverse events and/or serious adverse events related to the study device, PregSense™, in pregnant women with a singleton pregnancy > 24 +0 gestational weeks.

9.2.3 Secondary Performance Measures

Uterine contractions as measured by PregSense™ versus the standard of care (i.e. CTG including TOCO recordings).

The parameters are measured continuously for a duration of 30 minutes with data sampling taken at 1-minute intervals in parallel with both study devices.

Three blinded assessors will review the recordings and determine for each time point whether a contraction occurred.

9.3 Success Criterion

The study will be deemed successful if the limits of agreement (LOA's) for FHR and MHR between PregSense and the standard of care device are within the interval [-7, 7] Bpm.

In the literature, the limits of agreement for both FHR and MHR with FSE, abdominal fetal ECG and ultrasound were clinically evaluated showing that the abdominal fetal ECG limits of agreement is (± 1.96 SD) 8.40; -8.72¹¹.

9.4 Sample Size Justification

The company intends to recruit a minimum of 50 subjects for this study. An attempt will be made to include 5 subjects with contractions per site.

The minimum recommended number of measurements for a method comparison study as per EP09-A3: "Measurement Procedure Comparison Bias Estimation Using Patient Samples Approved Guideline – Third Edition") is a sample size of 40 laboratory samples (subjects in our case). The devices will record for 30 minutes with data sampling at 1-minute intervals, i.e. each subject may have up to 30 minutes measurements of FHR and MHR available for analysis, but no less than 1 minute of paired corresponding detection data with both modalities. We expect that on average there will be at least 5 paired measurements per subject. Therefore, if at least 50 subjects are recruited for the study there will be up to 1000 measurements of heart rate with both devices and no less than 250.

¹¹ http://beijingyes.com/download/Holter_2_Accuracy_and_reliability_of_fetal_heart_rate_monitoring.pdf

In addition, from preliminary company data the mean difference between FHR measurements with two methods was 0.695BPM (SD= 1.15BPM), using the sample size equation from Lu MJ, Zhong WH, Liu YX, Miao HZ, Li YC, Ji MH (2016) Sample size for assessing agreement between two methods of measurement by Bland-Altman method. The International Journal of Biostatistics 12: issue 2 (pp. 8), we find that with a sample size of at least 50 subjects the acceptance criterion can be met at a 5% level of significance and with 90% power even if the standard deviation is almost twice as high as seen in the feasibility study.

An acceptable outcome for the secondary performance measure of Uterine contractions agreement is 85%, in order to estimate this parameter with a two-sided 95% exact binomial confidence interval having a half-width of $\pm 10\%$ at least 65 contractions are required. If each subject experience at least 2 contractions and the within subject correlation is moderate ($r=0.5$) then a sample size of 44 women will be sufficient to measure this endpoint with acceptable reliability.

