16 REFERENCES42

Table of figures:

Figure 1 PregSense ME (self-monitoring)..... 15

Figure 2 PregSense MD (remote monitoring)..... 16

Figure 3 PregSense MD (Medical center/Clinic environment)..... 16

Figure 4 Block Diagram of PregSense™ Components 17

Figure 5 Schematic Illustration of the Wearable Sensory Belt 19

Figure 6 PregSense data flow of the cloud 20

Figure 7 PregSense data flow from the cloud to the App 21

Figure 8 Recording Session Flow 39

Figure 9 Pivotal study Application Flow..... 40

Figure 10 Pivotal Clinical Trial Setup Flow:..... 41

**CLINICAL STUDY EVALUATING THE SAFETY OF THE NON-INVASIVE
PREGSENSE™ AND COMPARATIVE PERFORMANCE OF PREGSENSE™
VERSUS CTG IN PRENATAL MONITORING OF PREGNANT SUBJECTS**

Ref. No.: CLP1000

Rev. 05

Page 8 of 42

STUDY SYNOPSIS

Protocol Number	CLP1000
Study Title:	Clinical Study Evaluating the Safety of PregSense™ and Comparative Performance of PregSense™ versus CTG in Prenatal Monitoring of Pregnant subjects.
Number of Centers:	Up to 5 centers with possible extension
Countries:	Israel, Germany and USA
Study Duration:	The expected total duration of the study for each subject is up to 2 hours as follows: Enrollment: Gestational age >32+0 weeks Data collection: 1 st data collection session and optional additional sessions between the initial session and up to labor.
Total Study Duration:	~24 months
Expected Subject Enrollment:	The total expected enrollment is up to 200 subjects.
Study Population:	Pregnant women with singleton gestation > 32+0 weeks of pregnancy.
Study Objectives:	The primary objective of this research is to assess the agreement between PregSense™ data collection, and values measured via the standard of care used for prenatal monitoring (i.e. CTG) and to assess the safety of PregSense™.

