5.1.1 Screening

An initial subject screening evaluation will be done during consultation or on the phone in order to identify eligible candidates. This will be applied on all trial subjects.

The candidate will then be invited to the first visit in which, confirmation of the eligibility criteria will be performed. All screened subjects will be identified by a subject number and will sign an Informed Consent Form (ICF) prior to any study procedure initiation. Each subject will receive a detailed explanation about the study purpose and procedure; at the end of the explanation, the

subject will sign an ICF. An authorized study personnel will take the subject's measurements and vital signs and will confirm that the subject meets the Inclusion/ Exclusion criteria.

Sites will make all efforts to maintain a balanced distribution of subjects across the different weeks of pregnancy. An attempt will be made to include at least 5 women with contractions in each site.

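### In 9.4 the 65 contractions and the 44 women do not agree at 2 contractions per woman and r = 0.5, and no recruitment provision secures either number

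*Combined protocol and SAP*

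**What the plan says.** Section 9.4 sizes the secondary endpoint in two steps. For 85% agreement and a two-sided 95% exact binomial interval with a half-width of 10 points, "at least 65 contractions are required". It then turns contractions into women: "If each subject experience at least 2 contractions and the within subject correlation is moderate" (r = 0.5), "then a sample size of 44 women will be sufficient to measure this endpoint with acceptable reliability". No formula is given for either step.

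On recruitment, 9.4 says "The company intends to recruit a minimum of 50 subjects for this study" and "An attempt will be made to include 5 subjects with contractions per site". Section 5.1.1 words the second point slightly differently: "An attempt will be made to include at least 5 women with contractions in each site". The Study Synopsis gives "Up to 5 centers with possible extension", total enrolment of up to 200, and "optional additional sessions between the initial session and up to labor".

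Sections 6.1 and 6.2 do not make contractions a condition of entry, and the balancing in 5.1.1 and 7.1.1 concerns gestational age. Under 9.6.4.2 the denominator for positive agreement is the number of contractions identified by the standard of care, so a woman without any adds nothing to it.

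**The concern.** Two things look wrong. First, the usual inflation for clustering does not take 65 contractions to 44 women at the stated cluster size and correlation, so at least one printed figure cannot stand. Second, the number of women in 9.4 has to be read as women who each have at least 2 contractions during the paired recording. Recruitment is not planned in those terms.

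At stake is how precisely contraction agreement will be known. Section 9.6.4.2 judges acceptability on a point estimate of 85%, so the interval around that estimate is what shows how firm it is. Its planned width should rest on figures that agree with each other and on a recruitment rule that aims at them.

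**Working it through.** **Inputs.** All are from 9.4 unless noted: agreement 85%; exact two-sided 95% interval; half-width 10 points; 65 contractions; m = 2 contractions per woman (the stated minimum); r = 0.5; 44 women; minimum 50 subjects; 5 women with contractions per site. From the Synopsis: up to 5 centers and up to 200 subjects.

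**Formulas.** Design effect DE = 1 + (m − 1)r. Effective contractions = women × m / DE. Women needed = contractions × DE / m, rounded up. Half-width = (upper − lower)/2 of the Clopper-Pearson interval at 85%, allowing non-integer counts; this averages the two unequal arms.

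**Step 1: trying to reproduce 44 from 65.** DE = 1 + (2 − 1) × 0.5 = 1.5.
- 65 × 1.5 / 2 = 48.75, i.e. 49 women. The stated 44 is not reproduced.
- In reverse, 44 × 2 / 1.5 = 58.7 effective contractions, short of 65. With 49 women: 49 × 2 / 1.5 = 65.3.
- With 3 contractions per woman, DE = 2.0 and 65 × 2 / 3 = 43.3, i.e. 44. But 9.4 claims sufficiency from 2.

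**Step 2: trying to reproduce 65.**

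| Contractions (effective) | Exact 95% interval at 85% | Half-width |
|---|---|---|
| 57 | 73.1% to 93.1% | 10.01 |
| 58 | 73.2% to 93.0% | 9.91 |
| 58.7 (44 women) | 73.3% to 93.0% | 9.86 |
| 65 | 74.0% to 92.7% | 9.34 |
| 65.3 (49 women) | 74.0% to 92.6% | 9.31 |

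The average exact half-width falls to 10 points at 58 contractions, not 65. Other criteria do not give 65 either: Wald 49, Wilson 49, Wald with continuity correction 59, and a lower arm of at most 10 points 77. Putting 58 into the second step gives 58 × 1.5 / 2 = 43.5, i.e. 44 women. So 44 fits the stated precision and 65 does not fit 44. The documents do not show which figure was intended.

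**Step 3: recruitment.** 5 women × 5 sites = 25 if all five sites open; three sites would give 15. The minimum of 50 subjects exceeds both 44 and 49, but it is not limited to women with contractions. Reaching the figure within 50 would need 44/50 = 88% (or 49/50 = 98%) of subjects to have at least 2 contractions in the recording. Within 200 it would need 44/200 = 22% (or 49/200 = 24.5%).

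**Step 4: precision if only 25 women contribute 2 contractions each.** This is a condition, not a forecast.
- Total contractions: 25 × 2 = 50. Effective at r = 0.5: 50 / 1.5 = 33.3.
- Exact interval 68.4% to 94.9%, half-width 13.3.
- Wald-type, closer to the model-based interval planned in 9.6.4.2: 1.96 × √(0.85 × 0.15 / 33.3) = 12.1 points. The same formula gives 9.1 for 44 women.
- With no correlation (r = 0, n = 50) the exact half-width is 10.7.
- With more contractions and a lower correlation the target can be met: 25 women, 3 each, r = 0.1 gives 62.5 effective contractions and 9.5 points.

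**The case against.** The strongest reply is that nothing is lost. On the plan's own inputs 44 women give 9.9 points, so the promised precision is met. The minimum of 50 subjects exceeds 44 and 49, and enrolment may reach 200. Five per site is an attempt, worded as a minimum in 5.1.1, and it caps nothing. Centers may be added, and optional repeat sessions could bring in more contributing women. The sentence in 9.4 is also openly conditional on each subject having at least 2 contractions.

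Much of this stands, and it rules out three stronger readings. A reader might infer that 44 is simply an error for 49. The documents do not support that, because 65 is itself not reproduced and 44 follows from 58. A reader might infer that the stated inputs fail to deliver ±10 points; they do deliver it, narrowly. A reader might also infer that the trial will have only 25 women with contractions. The documents give no contraction prevalence, so 25 is neither a forecast nor a guaranteed floor.

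What does not fall away is that 65 and 44 cannot both stand at 2 per woman and r = 0.5. Nor does any provision, whether the minimum of 50, the ceiling of 200, extra centers or optional sessions, refer to the contraction target. The plan does not say whether optional sessions enter the contraction analysis.

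**Conclusion.** The point holds in two parts. First, 65 contractions and 44 women are mutually inconsistent at the stated inputs: 65 needs 49 women (5 more, or 11%), and 44 women correspond to 58.7 effective contractions. This rests on the standard design effect with exactly 2 contractions per woman. It is a fault in the derivation; it does not by itself break the precision target.

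Second, and of more practical consequence, the only contraction-specific provision is an attempt at about 25 women if five sites open, against the 44 or 49 women with at least 2 contractions each that the calculation needs. If only 25 contributed 2 each at r = 0.5, the half-width would be about 13 points (exact) or 12 (Wald-type) instead of 10. Whether that happens cannot be told from the documents.

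The weight is limited. The endpoint is secondary, it is outside the success criterion in 9.3, and 9.6.4.2 has the achieved interval reported. The change is worth making because a printed sample-size figure is inconsistent and cheap to correct.

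**What to change.** In 9.4, state the method behind the number of contractions and print the design-effect formula. Then choose one of two corrections:
- keep 65 contractions and restate 44 as 49 women; or
- keep 44 women and restate 65 as about 58 effective contractions.

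In 5.1.1 and 9.4, align the recruitment wording with the corrected figure in one of two ways:
- set a study-wide target for women with at least 2 contractions in the paired recording, within the planned enrolment of up to 200, and say whether optional sessions count towards it; or
- keep 5 per site and state the precision it would give: about ±13 points exact, or about ±12 Wald-type, if 25 women contribute 2 contractions each at r = 0.5.

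The cost is a text change to two sections. The first recruitment option may alter the mix of women enrolled, without raising the ceiling of 200. The second means stating a less favourable precision for a secondary endpoint.
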